Differential treatment effect, also referred to as heterogeneity of treatment effect, refers to differences in efficacy as a function of pre-existing patient characteristics such as baseline variables. This is often assessed by forming subgroups or using an interaction analysis. Supplemental interaction analyses will be implemented to examine the potential for differential treatment effect. Differential treatment effect will be examined in strata defined by (but not limited to) respiratory support category at enrollment, status of co-enrollment in an open label clinical trial of antiplatelet agents (ACTIV-4a), age category, SARS-CoV-2 vaccination status, and passive immunity status, co-enrollment in other studies, and concomitant use of study drug and other medications during the study drug administration period. These analyses will be implemented using a modified version of the primary analysis method, where the treatment effect will be estimated separately for each level of the stratification variable. Stratum-specific treatment effect estimates will be presented with 95% Bayesian confidence interval. No formal hypothesis testing will be implemented for these analyses. Studies under this master protocol will be sized only for assessing efficacy using the primary analysis. Thus, there may be inadequate power to examine differential treatment.

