5 EFFICACY TESTING & FAMILYWISE TYPE-I ERROR CONTROL

Efficacy regarding the primary outcome and each key secondary outcome will be tested using a one-sided method that ensures no more than a 2.5% chance of a type-I error. The fixed-sequence method will be used to control the familywise type-I error probability at 2.5% for the family of primary and key secondary outcomes.¹ Specifically, a conclusion of efficacy regarding the primary outcome will be required prior to testing the first designated key secondary outcome. Each subsequent key secondary outcome, in the designated order, will take place only if the preceding key secondary outcome demonstrates efficacy. This approach provides strong control of the familywise type-I error probability at 2.5% for the family of primary and key secondary outcomes. No other statistical hypothesis tests will be made regarding other secondary, safety, or exploratory outcomes. P-values associated with certain null hypothesis tests may be provided for descriptive purposes, or to fulfill special requests, e.g., for DSMB safety assessments.

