6.3 Planned Interim and Final Analyses, Early Stopping, and Type-I Error Control

Two planned interim analyses will occur separately for each study arm when the number of participants with complete 28-day follow-up (or were deceased, withdrawn, or lost-to-follow-up by day 28) reaches 33% and 67% of maximum enrollment for that arm. Interim analyses will be executed by unblinded personnel only. Participant records that inform the primary outcome must undergo monitoring prior to interim (and final) analysis. At each interim analysis, a study arm may be stopped early if there is evidence for inferiority/harm. Enrollment in the trial will be stopped early if the posterior probability for inferiority/harm exceeds 0.95.

Final analysis will occur once enrollment, follow-up, and the required monitoring are completed. Should additional data be collected after enrollment is halted at an interim analysis, the final analysis will incorporate this additional data. If the trial was stopped early at an interim analysis due to evidence of inferiority/harm, a conclusion of inferiority/harm will be indicated if the posterior probability for inferiority/harm remains greater than 0.95 at the final analysis. If the trial was not stopped early at an interim analysis due to evidence of inferiority/harm, efficacy will be indicated if the posterior probability for efficacy regarding the primary outcome exceeds a threshold as follows: For studies under this master protocol, the efficacy threshold was selected using statistical simulation to ensure a type-I error probability of 2.5% for each study arm. In all other scenarios, the trial is inconclusive.

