
Co-enrollment in other studies testing COVID-19 therapeutics may occur. Co-enrollment may affect the treatment effect estimates if there is effect modification associated with co-enrollment. We expect co-enrollment to occur in fewer than 5% of patients enrolled in the trial. However, because the decision to co-enroll is not affected by the treatment assignment in ACTIV 4 Host Tissue, co-enrollment will not favor any particular treatment. In addition, due to its rarity, we expect co-enrollment to have little impact on the estimated treatment effects, even when there is effect modification.

Differential treatment effect, also referred to as heterogeneity of treatment effect, refers to differences in efficacy as a function of pre-existing patient characteristics such as baseline variables. This is often assessed by forming subgroups or using an interaction analysis. Supplemental interaction analyses will be implemented to examine the potential for differential treatment effect. Differential treatment effect will be examined in strata defined by (but not limited to) respiratory support category at enrollment, status of co-enrollment in an open label clinical trial of antiplatelet agents (ACTIV 4a), age category, SARS-CoV-2 vaccination status, passive immunity status, co-enrollment in other studies, and concomitant use of study drug and

other medications during the study drug administration period. These analyses will be implemented using a modified version of the primary analysis method, where the treatment effect will be estimated separately for each level of the stratification variable. Stratum-specific treatment effect estimates will be presented with 95% Bayesian confidence interval. No formal hypothesis testing will be implemented for these analyses. Studies under this master protocol will be sized only for assessing efficacy using the primary analysis. Thus, there may be inadequate power to examine differential treatment.

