6.6 Sample Size and Decision Thresholds

The maximum number of participants to be enrolled in sub studies under the Master Protocol is 600 participants per trial, resulting in approximately 300 patients per active treatment arm, and 300 patients in the matching placebo arm. The placebo arm will be shared across all active treatment arms. We expect placebo participants to continue to accrue for as long as there are additional treatments to test and cases to enroll.

Type-I error and power regarding the analysis of the primary outcome was assessed based on the pooled (across all active and placebo arms) distribution of the primary outcome among the first 100 participants to complete follow-up and monitoring. The efficacy threshold was identified using statistical simulation under the null hypothesis to ensure the study operating characteristics achieve design specifications. Pooled and blinded summaries of oxygen-free days at day 28 were used to approximate the distribution of the oxygen free days in the placebo group. Based on these data, the anticipated frequency distribution, mean, and median of oxygen-free days (OFDs) for the placebo group, and for the treatment group under hypothetical effect sizes computed using the PO model are displayed in the table below.

OFDs / Odds Ratio	Placebo	Inferiority		Superiority						
		0.67	0.80	1.40	1.45	1.50	1.55	1.60	1.65	1.70
Mean	8.8	6.6	7.5	10.8	11.1	11.3	11.5	11.7	11.9	12.0
Median	0	0	0	6.5	7.5	9.0	10.0	10.5	12.5	14.5
P(OFDs \geq 22)	0.19	0.14	0.16	0.25	0.26	0.26	0.27	0.28	0.29	0.29
Proportion:										
-1 (death)	0.235	0.316	0.279	0.181	0.176	0.171	0.166	0.162	0.158	0.154
0	0.296	0.314	0.309	0.268	0.264	0.261	0.257	0.254	0.251	0.247
1	0.006	0.006	0.006	0.006	0.006	0.006	0.006	0.006	0.006	0.006
---	---	---	---	---	---	---	---	---	---	---
27	0.050	0.034	0.041	0.069	0.072	0.074	0.076	0.078	0.081	0.083
28	0.000	0.000	0.000	0.000	0.000	0.000	0.000	0.000	0.000	0.000

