Simulation under the null hypothesis was used to select the efficacy threshold for the final analysis. The efficacy threshold was selected to ensure no more than 2.5% type-I error. In this simulation, 10000 replicates were used to ensure ~0.31% simulation margin of error in estimating the type-I error rate. The efficacy threshold was identified as 0.976. A final analysis will occur once enrollment, follow-up, and the required monitoring are completed for all participants. Should additional data be collected after enrollment is halted at an interim analysis, the final analysis will incorporate this additional data. If enrollment was halted at an interim analysis due to evidence of inferiority/harm, a conclusion of inferiority/harm will be indicated if the posterior probability for inferiority/harm remains greater than 0.95 at the final analysis. If the trial was not stopped early at an interim analysis due to evidence of inferiority/harm, efficacy will be indicated if the posterior probability for efficacy regarding the primary outcome exceeds 0.976 at the final analysis. If neither condition is met for a conclusion of efficacy or inferiority/harm at the final analysis, the trial is inconclusive. The efficacy and inferiority/harm thresholds will be applied as described in the table below.

Analysis	Condition	Action
Interim analysis	Inferiority/harm probability > 0.950	Halt enrollment
Final analysis	Inferiority/harm probability \leq 0.950 at all interim analyses and efficacy probability > 0.976	Conclude efficacy
Final analysis	Inferiority/harm probability > 0.950	Conclude inferiority/harm

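### The interaction analyses specify stratum-specific odds ratios with 95% intervals but no between-stratum contrast, which is the quantity that measures differential treatment effect

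*SAP*

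**What the plan says.** SAP 6.5 describes differential effect as efficacy that varies with patient characteristics present beforehand. It then commits to an analysis of it: "Supplemental interaction analyses will be implemented to examine the potential for differential treatment effect". The factors listed include respiratory support at enrollment, age category, vaccination status, passive immunity and co-enrollment.

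The method is a modified form of the primary analysis. In Protocol 8.6.4, with the same text in SAP 6.5, "the treatment effect will be estimated separately for each level of the stratification variable". The reporting rule is: "Stratum-specific treatment effect estimates will be presented with 95% Bayesian confidence interval".

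Both sections add that these analyses involve no formal testing and may lack power. Neither names an interaction coefficient, a ratio of ORs or any other comparison between levels, and neither says how the stratum intervals are to be read. Protocol 7.6 raises the same kind of question for co-enrollment, asking whether it alters the effect of active drug against placebo.

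**The concern.** The question is whether the OR differs between levels of a factor, and the quantity that answers it is the ratio of the stratum ORs. The specified output is one OR per level, each with its own interval. Such an interval shows how well the effect in that level is known. It does not show how far the levels differ.

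A table of this kind is easily read by asking which intervals exclude 1. Under that reading a uniform effect can look like benefit confined to one group, because each stratum has less information than the whole trial. Unequal strata make this more likely, and co-enrollment is the extreme case: the documents expect fewer than 5% of patients there, which is fewer than 30 of 600. It is also unclear whether the separate estimates come from separate fits or from one model with an interaction term.

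At stake is how subgroup results are interpreted, not the trial's main conclusion.

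**Working it through.** **Inputs from the documents**
- SAP 5: "Efficacy regarding the primary outcome and each key secondary outcome will be tested using a one-sided method". SAP 6.3: "the efficacy threshold was selected using statistical simulation to ensure a type-I error probability of 2.5% for each study arm".
- SAP 6.6: "The efficacy threshold was identified as 0.976", so z(0.976) = 1.977.
- SAP 6.6: "The maximum number of participants to be enrolled in sub studies under the Master Protocol is 600 participants per trial", with "approximately 300 patients per active treatment arm, and 300 patients in the matching placebo arm".
- SAP 6.6 power table: 0.552, 0.631, 0.705, 0.782, 0.826, 0.856 and 0.893 at OR 1.40, 1.45, 1.50, 1.55, 1.60, 1.65 and 1.70.
- Co-enrollment below 5%. No other stratum share is given, so I assume splits from 50:50 to 95:5.

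**Step 1: the plan's own power figure.** The SAP gives no figure for the subgroup analyses, so I checked power at OR 1.65 (stated 0.856). The Whitehead formula gives 0.935 with complete outcomes and 0.903 with 12% loss. Simulating the SAP's 12% partial observation gives 0.896 without covariates and 0.883 with assumed covariate effects. None matches closely. The covariate effects and full outcome distribution are not published, so this does not show that the stated figure is wrong.

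I therefore used the standard error (SE) that the plan's table implies: SE = log(OR) / (z(0.976) + z(power)). At OR 1.65 this is 0.501 / (1.977 + 1.063) = 0.165. The seven entries give 0.159 to 0.165, and a single SE of 0.162 returns all seven powers within 2 percentage points. Interim stopping can be ignored here: the table's probability of an inferiority conclusion is at most 0.003 at these ORs.

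**Step 2: disagreement between strata under a uniform OR.** For a stratum with share f, SE_f = SE/√f. The probability that its 95% interval lies above 1 is p_f = Φ(log(OR)/SE_f − 1.96). Two strata disagree with probability p1(1 − p2) + p2(1 − p1).

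With SE 0.163 and OR 1.65:
- 50:50: SE_f = 0.163 × √2 = 0.231, p = Φ(2.17 − 1.96) = 0.584, disagreement 2 × 0.584 × 0.416 = 0.49.
- 95:5: SE_f = 0.167 and 0.729, p = 0.850 and 0.102, disagreement 0.850 × 0.898 + 0.102 × 0.150 = 0.78.

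Across SE 0.162 to 0.165:

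| Common OR | Split | Disagree |
|---|---|---|
| 1.00 | 50:50 | 0.05 (0.095 if intervals below 1 also count) |
| 1.25 | 50:50 | 0.27 |
| 1.40 | 50:50 | 0.42–0.43 |
| 1.55 | 50:50 | 0.50 |
| 1.65 | 50:50 | 0.48–0.49 |
| 2.00 | 50:50 | 0.24–0.26 |
| 1.65 | 70:30 | 0.55 |
| 1.65 | 80:20 | 0.63 |
| 1.65 | 90:10 | 0.72–0.73 |
| 1.65 | 95:5 | 0.77–0.78 |
| 1.65 | three strata | 0.73–0.79 |

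The three-strata row covers splits from equal thirds to 60:30:10; the primary model groups baseline WHO score in three.

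**Step 3: the direct contrast.** SE of the log ratio of ORs = SE × √(1/f1 + 1/f2). Under a uniform effect its 95% interval excludes 1 in 5% of trials by construction, whatever the common OR. Separate proportional odds fits to simulated trials at OR 1.65 gave 4.8% (150/150 per arm) and 5.3% (220/80 per arm).
- 50:50: SE 0.163 × 2 = 0.326. The interval is the estimate times or divided by exp(1.96 × 0.326) = 1.9. A ratio of exp(2.80 × 0.326) = 2.5 is needed for 80% power.
- 95:5: SE 0.163 × √(1/0.95 + 1/0.05) = 0.748. A ratio of exp(2.80 × 0.748), about 8, is needed for 80% power.

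**The case against.** The strongest reply is that nothing in the plan adopts the reading rule behind Step 2. A reader might infer that the intervals are meant to be compared with 1, or that a contrast is ruled out. The documents support neither: they name no reference value and no criterion for heterogeneity, and they are silent on a contrast. An effect estimated for each level is compatible with a single model that already contains a treatment-by-factor term.

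A reader might also infer that the stratum output cannot inform on heterogeneity at all. That goes too far. An approximate ratio can be recovered from the difference in log ORs, with SE √(SE1² + SE2²).

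Nor should the contrast be oversold. At the SE implied by the power table (about 0.162), true ORs of 1.0 and 2.3 would give a ratio interval excluding 1 in about 73% of trials with equal strata and about 62% with 220/80 per arm. For co-enrollment the contrast would say almost nothing, and SAP 6.5 already expects co-enrollment to have little impact.

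All of this stands, and it limits the point. It does not supply the missing quantity. Disclaiming tests and admitting low power do not replace an estimate of the difference, and a ratio with an interval is just as descriptive as the stratum ORs.

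**Conclusion.** The point holds as an omission: the plan promises interaction analyses and does not specify the estimate that answers the question. It does not follow that a uniform effect will look heterogeneous in half of trials, although a reader might infer that. A figure near one half needs a reader who treats discordant intervals as heterogeneity, near-equal strata and a common OR of about 1.4 to 1.7. It falls to 5–10% with no effect and to about a quarter at OR 1.25 or 2.0. At OR 1.65 it rises above half with unequal strata or three strata.

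The figures also assume full enrollment, equal information per patient across strata and normal approximations, which are rough for a stratum of fewer than 30. Shares other than the co-enrollment bound are mine. These analyses feed no threshold, stopping rule or key secondary test, so the primary conclusion is unaffected. The change is worth making because it is cheap and reports the quantity asked for.

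**What to change.** In SAP 6.5 and Protocol 8.6.4, for each baseline factor:
- fit the primary proportional odds model with a treatment-by-factor term, in one model on the full mITT set;
- report the ratio or ratios of ORs between levels with 95% credible intervals, beside the stratum-specific ORs;
- state that differential effect is judged descriptively from the ratio and not from whether individual stratum intervals include 1, with no test and no threshold.

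The cost is a few sentences and one added column in the subgroup table. No new data are needed. The ratio intervals will be wide, especially for co-enrollment, and will show openly how little the trial can say about subgroups. Concomitant medication during the treatment period is also on the list but is not a baseline factor, so this change does not cover it.

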6.6 Sample Size and Decision Thresholds

The maximum number of participants to be enrolled in sub studies under the Master Protocol is 600 participants per trial, resulting in approximately 300 patients per active treatment arm, and 300 patients in the matching placebo arm. The placebo arm will be shared across all active treatment arms. We expect placebo participants to continue to accrue for as long as there are additional treatments to test and cases to enroll.

Type-I error and power regarding the analysis of the primary outcome was assessed based on the pooled (across all active and placebo arms) distribution of the primary outcome among the first 100 participants to complete follow-up and monitoring. The efficacy threshold was identified using statistical simulation under the null hypothesis to ensure the study operating characteristics achieve design specifications. Pooled and blinded summaries of oxygen-free days at day 28 were used to approximate the distribution of the oxygen free days in the placebo group. Based on these data, the anticipated frequency distribution, mean, and median of oxygen-free days (OFDs) for the placebo group, and for the treatment group under hypothetical effect sizes computed using the PO model are displayed in the table below.

OFDs / Odds Ratio	Placebo	Inferiority		Superiority						
		0.67	0.80	1.40	1.45	1.50	1.55	1.60	1.65	1.70
Mean	8.8	6.6	7.5	10.8	11.1	11.3	11.5	11.7	11.9	12.0
Median	0	0	0	6.5	7.5	9.0	10.0	10.5	12.5	14.5
P(OFDs \geq 22)	0.19	0.14	0.16	0.25	0.26	0.26	0.27	0.28	0.29	0.29
Proportion:										
-1 (death)	0.235	0.316	0.279	0.181	0.176	0.171	0.166	0.162	0.158	0.154
0	0.296	0.314	0.309	0.268	0.264	0.261	0.257	0.254	0.251	0.247
1	0.006	0.006	0.006	0.006	0.006	0.006	0.006	0.006	0.006	0.006
---	---	---	---	---	---	---	---	---	---	---
27	0.050	0.034	0.041	0.069	0.072	0.074	0.076	0.078	0.081	0.083
28	0.000	0.000	0.000	0.000	0.000	0.000	0.000	0.000	0.000	0.000

Based on these data and effect size scenarios, a series of statistical simulations were implemented to examine the operating characteristics of the statistical study design described above, including the plan for randomization, statistical analysis method, interim analysis, and final assessments of efficacy using the odds ratio. In each simulation, participant age group, sex, and baseline WHO COVID severity score were randomly sampled with replacement from the values observed, and their effects on the primary outcome were simulated to match the estimated effects of age group, sex, and WHO score on the primary outcome among the first 100 participants. In order to assess the potential impact of attrition and loss-to-follow-up, partially observed oxygen free days were simulated to match the observed frequency of partially observed outcomes, which occurred in 12% of the first 100 participants. To encode attrition, a subset of the simulated study participants was selected at random, each with probability 0.12.

The primary outcome for each selected participant was encoded as partially observed by assuming that oxygen free days may have taken any value between -1 and a randomly sampled value ranging from the simulated oxygen free days to 28. For example, if the simulated oxygen free days is 10, then a value between 10 and 28 is sampled uniformly at random and this value is treated at the upper limit for the partially observed oxygen free days. This pattern of partially observed oxygen free days closely resembles the patterns observed among the first 100 participants. All simulation analyses, including those associated with interim and final assessment of efficacy and inferiority were implemented using the methods described above for the analysis of the primary outcome.

Simulation under the null hypothesis was used to select the efficacy threshold for the final analysis. The efficacy threshold was selected to ensure no more than 2.5% type-I error. In this simulation, 10000 replicates were used to ensure ~0.31% simulation margin of error in estimating the type-I error rate. The efficacy threshold was identified as 0.976. A final analysis will occur once enrollment, follow-up, and the required monitoring are completed for all participants. Should additional data be collected after enrollment is halted at an interim analysis, the final analysis will incorporate this additional data. If enrollment was halted at an interim analysis due to evidence of inferiority/harm, a conclusion of inferiority/harm will be indicated if the posterior probability for inferiority/harm remains greater than 0.95 at the final analysis. If the trial was not stopped early at an interim analysis due to evidence of inferiority/harm, efficacy will be indicated if the posterior probability for efficacy regarding the primary outcome exceeds 0.976 at the final analysis. If neither condition is met for a conclusion of efficacy or inferiority/harm at the final analysis, the trial is inconclusive. The efficacy and inferiority/harm thresholds will be applied as described in the table below.

Analysis	Condition	Action
Interim analysis	Inferiority/harm probability > 0.950	Halt enrollment
Final analysis	Inferiority/harm probability \leq 0.950 at all interim analyses and efficacy probability > 0.976	Conclude efficacy
Final analysis	Inferiority/harm probability > 0.950	Conclude inferiority/harm

Using the selected efficacy and inferiority/harm thresholds, the results of 10000 simulations under the null hypothesis, and 1000 simulations per inferiority/efficacy scenario are summarized in the table below. In these simulations, the type-I error probability was 2.47%. The frequency of stopping early for inferiority under the null was 8.6% (5.3% at the first interim analysis, and 3.2% at the second interim analysis). A *maximum sample size of 600 participants per trial provides greater than 85% power to detect an odds ratio of 1.65, corresponding to a 3.1-day difference in mean OFDs, and a 7.8 percentage point reduction in 28-day mortality*. Differences larger than 2 ventilator-free days on average have been considered clinically important in prior trials.²⁻⁴ Thus, the minimum detectable effect with 85% power (MDE85) is an odds ratio of 1.65. The frequency of stopping early for inferiority when there was an effect larger than OR=1.40 was <1%. When the simulated treatment was inferior/harmful relative to placebo, at OR=0.67, a conclusion of inferiority/harm occurred in 83.3% of simulated trials (39.1% at the first interim, 27.9% at the second interim, and 16.3% at the final analysis), and the average half-sample size was 193.9 per arm.

	Null	Inferiority		Superiority						
	1.00	0.67	0.80	1.40	1.45	1.50	1.55	1.60	1.65	1.70
OFDs / Odds Ratio	1.00	0.67	0.80	1.40	1.45	1.50	1.55	1.60	1.65	1.70
Pr(Efficacy)	0.025	0.000	0.001	0.552	0.631	0.705	0.782	0.826	0.856	0.893

OFDs / Odds Ratio	Null	Inferiority		Superiority						
	1.00	0.67	0.80	1.40	1.45	1.50	1.55	1.60	1.65	1.70
Pr(Inferiority)	0.108	0.833	0.508	0.003	0.002	0.001	0.000	0.000	0.001	0.000
Pr(Inconclusive)	0.867	0.167	0.491	0.445	0.366	0.294	0.218	0.173	0.143	0.107
Average(N/2)	286.1	193.9	242.0	299.4	299.8	299.8	300.0	300.0	299.8	300.0

In order to characterize the effect of uncertainty in the distribution of the OFD outcome on the type-I error probability, simulations under the null hypothesis were twice repeated assuming a “mild” and “severe” distribution for the OFD outcome. The mild and severe distributions were selected such that the unadjusted mortality rate ranged $\pm 3\%$ relative to the initial simulation. The results of 1000 simulations in each of the mild placebo and severe placebo scenarios are summarized in the table below. In these simulations, the type-I error probability was 2.5% and 2.3%.

	Severe	Mild
	OR = 1.00	OR = 1.00
Mortality rate	0.266	0.206
Pr(Efficacy)	0.023	0.025
Pr(Inferiority)	0.0.119	0.117
Pr(Inconclusive)	0.858	0.858
Average(N)	284.0	286.4

Prior to the start of enrollment, initial sample size assessments were based on pooled and blinded summaries of OFDs from the PassItOn (convalescent plasma) trial of patients hospitalized for COVID-19. The inclusion and exclusion criteria for PassItOn are similar to that for ACTIV 4 Host Tissue. In these initial assessments, the estimated MDE85 was OR=1.55. Statistical power was subsequently reassessed using OFDs summaries in the first 100 participants enrolled in ACTIV 4 Host Tissue, which demonstrated a more severe distribution relative to PassItOn participants (23.6% vs 17.6% mortality). The estimated MDE85 was OR=1.65 at the time of sample size reassessment. However, additional information from blinded summaries of the first 200 enrolled participants are consistent with the distribution of OFDs observed in PassItOn (18.6% vs 17.6% mortality). After discussion of these findings among the blinded study investigators and study sponsor, it was determined that statistical power was sufficient and no sample size adjustment was warranted.

